#### **8.4.8    Subject Pregnancy**

Women of childbearing potential are not excluded from the study as long as adequate birth control methods are being used by the subject. However, if a woman becomes pregnant during

##### **CONFIDENTIAL AND PROPRIETARY**

This document contains information that is confidential and proprietary to Smith & Nephew PLC and Smith & Nephew, Inc. and is intended for use only by Smith & Nephew and its manufacturer. It shall not be reproduced or copied in whole or in part, nor shall the contents be disclosed by any means without prior written permission from Smith & Nephew, nor shall anyone make any use of it that is contrary to the expressed or implied wishes of Smith & Nephew.

Study Protocol—Device	
A Multicenter, Post Market, Prospective Study Evaluating Safety and Efficacy of CONQUEST FN™ for the Treatment of Intracapsular Femoral Neck Fractures	Number: 18-3047-02
	Version: 2.0, 30Nov2018
	Page: Page 30 of 63

the study, S&N must be contacted immediately once the Investigator is made aware of the pregnancy. Pregnancy is not reportable as an adverse event; however, complications related to the pregnancy may be reportable as determined on a case-by-case basis. Pregnancy-related information will be collected until the end of the pregnancy.

## 8.5 STUDY METHODS AND MEASUREMENTS

All questionnaires should be completed prior to any other procedure at the time of the scheduled visit. The dates of all assessments should be recorded.

### 8.5.1 Visual Analogue Scale (VAS) for Pain

The Visual Analogue Scale is simply a line of fixed length, on which the subject marks their experience of pain with a single stroke of a pen.

At each specified visit, the subject will be asked to indicate their average level of pain from the operated hip over the prior 24 hours using a visual analog scale (VAS). The subject will record their level of pain on a 100 mm visual analog scale, similar to the one illustrated above. The scale will be marked 'no pain' on the left side of the scale and 'severe pain' at the right end of the scale. The subject will be instructed to place a vertical mark on the scale, using an ink pen.

The Investigator, or designee, will measure the distance (in millimeters) from the left end of the VAS scale to the vertical line drawn by the subject. This value will be entered in the subject's CRF as a measure of the pain associated with the operated hip.

### 8.5.2 EQ-5D-5L

The EuroQol EQ-5D-5L is a standardized instrument for use as a measurement of health outcome. It consists of a descriptive system with 5 dimensions (mobility, self-care, usual

#### **CONFIDENTIAL AND PROPRIETARY**

This document contains information that is confidential and proprietary to Smith & Nephew PLC and Smith & Nephew, Inc. and is intended for use only by Smith & Nephew and its manufacturer. It shall not be reproduced or copied in whole or in part, nor shall the contents be disclosed by any means without prior written permission from Smith & Nephew, nor shall anyone make any use of it that is contrary to the expressed or implied wishes of Smith & Nephew.

Study Protocol—Device	
A Multicenter, Post Market, Prospective Study Evaluating Safety and Efficacy of CONQUEST FN™ for the Treatment of Intracapsular Femoral Neck Fractures	Number: 18-3047-02
	Version: 2.0, 30Nov2018
	Page: Page 31 of 63

activities, pain/discomfort and anxiety/depression), which are each assigned five levels (no problems, slight problems, moderate problems, severe problems and extreme problems), as well as, a Visual Analogue Scale where subjects indicate a numerical value from 1-100 where 0 is the worst imaginable health state and 100 is the best imaginable health state.

The respondent is asked to indicate his/her health state by ticking (or placing a cross) in the box against the most appropriate statement in each of the 5 dimensions. This decision results in a 1-digit number expressing the level selected for that dimension. The digits for 5 dimensions can be combined in a 5-digit number describing the respondent's health state.

#### **8.5.3 Timed Up and Go (TUG)**

The Timed Up and Go Test assesses mobility, balance, walking ability, and fall risk in adults by measuring time, in seconds, that it takes the individual to stand from a chair, walk a distance of 10 feet, walk back to the chair, and sit down. The subject will perform the test in their everyday footwear with their walking aid (cane, walker), if applicable. The site will follow the guidelines provided by the Centers for Disease Control and Prevention recording the results on the form provided by the Sponsor.

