## 7.7 WITHDRAWAL

### 7.7.1 Withdrawal from Study

The Investigator **may** withdraw subjects from the study for many reasons, including, but not limited to, the following:

- subject noncompliance (e.g. did not follow instructions, took disallowed medications)
- subject lost to follow-up
- if the Investigator or the Sponsor stops the study for any reason and decides to withdraw subject(s) from the study
- concurrent illness
- Adverse Events/Adverse Device Effects
- any other significant reason identified by the Investigator
- in the event any component of the original hardware is revised/exchanged

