#### **8.4.7 Concomitant Medications and Therapies**

##### **CONFIDENTIAL AND PROPRIETARY**

This document contains information that is confidential and proprietary to Smith & Nephew PLC and Smith & Nephew, Inc. and is intended for use only by Smith & Nephew and its manufacturer. It shall not be reproduced or copied in whole or in part, nor shall the contents be disclosed by any means without prior written permission from Smith & Nephew, nor shall anyone make any use of it that is contrary to the expressed or implied wishes of Smith & Nephew.

Study Protocol—Device	
A Multicenter, Post Market, Prospective Study Evaluating Safety and Efficacy of CONQUEST FN™ for the Treatment of Intracapsular Femoral Neck Fractures	Number: 18-3047-02
	Version: 2.0, 30Nov2018
	Page: Page 29 of 63

A concomitant medication (e.g. drug, substance) and a concomitant therapy (e.g. physical therapy, TENS Unit, massage) are recorded pre-operatively and at each visit through the subject's last study visit. The subject's ambulatory status will be documented pre-operatively and at each follow-up through the last study visit.

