### 9.1 GENERAL

The subject data will be described and summarised using the baseline demographic and medical variables, which include, but are not limited to, age, gender, ethnicity, medical and medication history, diagnostic factors as well as study process variables (e.g. AE and withdrawal(s)). Summary statistics will be given according to the nature of the variable, continuous or categorical. For continuous variables, the number of observations, mean, standard deviation, median, minimum, and maximum will be presented, while for categorical variables the number of observations, frequency, and percentages will be reported.

Primary, secondary, and exploratory outcome variables and derived variables will also be summarised accordingly. Parametric statistical tests will be used if the data are normally distributed and corresponding non-parametric tests will be considered if the data are not. Where necessary, suitable regression techniques will be used to adjust for confounding variables since the study is non-randomised. The results will be reported at 5% significance level and where appropriate 95% confidence intervals will be given.

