## 9.2 ANALYSIS POPULATIONS

- Intention to Treat population (ITT), including all subjects randomized into the study.
- Full analysis set population (FAS), following Intention to Treat principle including all subjects who were randomized into the study and attended at least one post-baseline assessment
- Safety Population (SAF), including all subjects who have received the IP or the control devices.
- Per-Protocol Population (PP), including all subjects in the full analysis set who have no significant protocol deviations and met the inclusion/exclusion criteria.

Statistical analysis will be performed using each of the patient populations as follows. Analysis of the primary, secondary and exploratory efficacy objectives will be performed separately using both the Full Analysis Set and the Per Protocol Population. All safety analyses will utilize the Safety Population.

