#### 9.4.2 Analysis of Secondary Endpoint(s)

The rate or mean of the following outcomes at 1 year post-operation will be reported:

- Intraoperative complications
- Radiographic outcomes including quality of fracture reduction
- Construct failure past typical femoral neck fracture healing period (past 6 months)
- Visual analogue scale (VAS) relating to pain at the fracture site
- Quality of Life (EQ-5D-5L)
- Time to return to full weight-bearing
- Ambulatory status from pre-injury to study completion
- Timed Up & Go
- Length of hospital stay
- Hospital readmission for any reason
- Device and surgery related adverse events
- Active straight leg raise (ASLR) assessment

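### The Timed Up & Go summary leaves out, without a count, subjects who attend but cannot do the test, so it overstates mobility if there are any

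*Combined protocol and SAP*

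**What the plan says.** Section 8.5.3 defines TUG by "measuring time, in seconds, that it takes the individual to stand from a chair, walk a distance of 10 feet", followed by the walk back and sitting down. The subject performs it "with their walking aid (cane, walker), if applicable", so needing an aid is not the same as being unable. Sites follow an external guideline, "recording the results on the form provided by the Sponsor". The section gives no code or score for a subject who cannot do the test.

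Table 8.4.1-1 schedules TUG at 6 weeks and at 3, 6 and 12 months. Section 9.4.2 lists it among 12 secondary outcomes with the instruction "The rate or mean of the following outcomes at 1 year post-operation will be reported". No rate is defined for TUG, so for a variable in seconds this means the mean. Section 9.1 adds a general rule: "For continuous variables, the number of observations, mean, standard deviation, median, minimum, and maximum will be presented". Section 9.2 says that efficacy analyses "will be performed separately using both the Full Analysis Set and the Per Protocol Population", but neither definition covers a visit that has no TUG time.

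The active straight leg raise (ASLR), done at the same visits, uses a scale from 0 to 5 on which 5 is inability. A subject who cannot raise the leg keeps a value and stays in the summary.

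**The concern.** For this test, being unable is the worst result. A summary of completed times leaves that result out and describes only the subjects who were able. The median under section 9.1 omits the same people. The number of observations falls when someone cannot do the test, but it falls equally when someone does not attend, so it does not reveal the cause.

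Inability is plausible here. Section 7.1 sets no upper age limit. Section 4.1 discusses adults over 70 and cites complication rates of 15–64% for displaced fractures. Time to full weight-bearing and ambulatory status are endpoints in their own right. A reader of the 1-year TUG figure would not know whether it describes all attending subjects or only those who could walk.

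**Working it through.** **The plan's own figure.** There is none to reproduce. The documents give no expected TUG mean, SD, precision or share unable. The arithmetic below is illustrative and rests on assumed inputs.

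**Step 1: who enters each summary.**

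| Subject at the 1-year visit | TUG mean, median, n (9.4.2, 9.1) | ASLR summary |
|---|---|---|
| Attends, completes the test | included | included |
| Attends, unable | no time, so absent and not counted | included at 5, the worst score |
| Does not attend | absent | absent |

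For TUG the second and third rows look identical. For ASLR they do not.

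**Step 2: illustration.** Assume completer times are lognormal with median 14 s and log-SD 0.45. Let f be the share of attending subjects who are unable, and z(p) the standard normal quantile.

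- Completer mean = 14 × exp(0.45²/2) = 14 × exp(0.10125) = 15.5 s. It does not contain f.
- Median with the unable ranked worst = 14 × exp(0.45 × z(0.5/(1 − f))).
- Upper quartile with the unable ranked worst = 14 × exp(0.45 × z(0.75/(1 − f))).

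At f = 0.10 the median uses z(0.556) = 0.140, giving 14 × exp(0.063) = 14.9 s. At f = 0.20 it uses z(0.625) = 0.319, giving 14 × exp(0.143) = 16.2 s.

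| Share unable (assumed) | Completer mean | Worst-rank median | Worst-rank upper quartile |
|---|---|---|---|
| 0% | 15.5 s | 14.0 s | 19.0 s |
| 10% | 15.5 s | 14.9 s | 21.6 s |
| 20% | 15.5 s | 16.2 s | 27.9 s |

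Of the 80 evaluable subjects in section 10, 10% would be 0.10 × 80 = 8 and 20% would be 16.

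**Step 3: other assumed distributions.** With lognormal completers of mean 12 s and SD 4 s, the worst-rank median is 11.4 s, 11.9 s and 12.6 s at 0%, 10% and 20% unable. With mean 15 s and SD 6 s it is 13.9 s, 14.7 s and 15.7 s. The direction is the same and the shift is again modest.

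**Step 4: a mean with an assigned time.** Giving unable subjects a ceiling time w, the mean is (1 − f) × m + f × w, where m is the completer mean. With m = 12 s:

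- f = 0.10: 10.8 + 3.0 = 13.8 s for w = 30 s, and 10.8 + 6.0 = 16.8 s for w = 60 s.
- f = 0.20: 9.6 + 6.0 = 15.6 s for w = 30 s, and 9.6 + 12.0 = 21.6 s for w = 60 s.

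A mean can therefore include these subjects, but the answer depends heavily on the chosen w. The worst-rank median needs no such choice as long as fewer than half are unable. The upper quartile needs fewer than a quarter, because 0.75/(1− f) must stay below 1.

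**The case against.** The strongest reply is that this is an omission that may already be closed. No sentence orders these subjects to be dropped. The sponsor's TUG form is not in the documents and may have a field for inability. Section 9 calls itself brief and promises a fuller SAP before database lock. This stands as a limit on what can be concluded. It does not remove the point: if the form does not capture inability while visits are under way, a later SAP cannot reliably recover it.

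A second reply is that subjects who cannot walk remain visible elsewhere. Section 8.4.7 states: "The subject's ambulatory status will be documented pre-operatively and at each follow-up through the last study visit". ASLR, time to full weight-bearing and the EQ-5D-5L mobility dimension add to this. That is true of the endpoint package as a whole, but none of these is linked to TUG or qualifies the TUG figure.

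A third reply is that the share is probably small. Walking aids are allowed, section 6.1.1 aims at people who are otherwise active, and the reported time point is 12 months. This may well be right, but the planned output could not show it.

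A reader might also infer three stronger things that the documents do not support:

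- That a mean in seconds can never include unable subjects. Step 4 shows that it can, at an assigned time.
- That the reported mean improves as more subjects become unable. With the completer distribution held fixed, it stays at 15.5 s; it merely fails to worsen.
- That TUG means at different visits are being compared on different subjects. No passage specifies an across-visit comparison of TUG; section 9.4.2 reports at 1 year.

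**Conclusion.** The point holds in a limited form. As written, every planned TUG figure is computed on completers, and attending subjects who cannot do the test are neither included nor counted. If there are any, the summary overstates mobility; if there are none, there is no bias.

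The size cannot be established from the documents. Under the assumed 14 s median and log-SD of 0.45, the worst-rank median is 0.9 s longer than the completer median at 10% unable and 2.2 s longer at 20%. Both shares are assumptions.

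The consequence is contained. TUG is one of 12 secondary endpoints in a single-arm, non-comparative study, with no TUG hypothesis or threshold. The reoperation endpoint and the sample size are untouched. The change is worth making because it is cheap and because ASLR already keeps unable subjects in its summary.

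**What to change.** 1. Unless the sponsor's form already does so, add two separate entries: "not done: unable" (because of mobility or the hip) and "not done: other".
2. In section 9.4.2, at 1 year and at any other visit where TUG is summarised (for example the interim summary in section 9.6), report the number and percentage of attending subjects unable to complete TUG. Report also the median and quartiles with those subjects ranked worst. Where a quartile falls among the unable, print it as unable.
3. Keep the mean among completers as a supporting figure, labelled as such.

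The denominator is attending subjects. It does not cover those who have left the study, for instance under the option in section 7.7.1 to withdraw a subject "in the event any component of the original hardware is revised/exchanged". They should be shown in the accountability report and not counted as unable.

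The cost is one form field and a few lines of analysis text. The downside is that a worst-rank median is less familiar to readers than a mean.

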#### **8.5.4 Assessment of Quality of Fracture Reduction**

The quality of the final fracture reduction will be defined using the criteria described by Upadhyay et al. Appropriate reduction will be defined as the principal compressive trabeculae measuring >160° in the AP view and <5° of posterior angulation in the lateral view. If reduction is acceptable in both views, it will be classified as grade I. Grade II will be indicative of one plane of malreduction, and grade III will be indicative of malreduction in both radiographic views.

Pre-operative radiographs will be reviewed and classified as displaced (e.g. Garden III & IV) or non-displaced (e.g. Garden I & II) femoral neck fractures by the Investigator at each site. Quality of fracture reduction will also be assessed post-operatively by the Investigator at each site.

#### **8.4.5 Active Straight Leg Raise (ASLR) Assessment**

#### **CONFIDENTIAL AND PROPRIETARY**

This document contains information that is confidential and proprietary to Smith & Nephew PLC and Smith & Nephew, Inc. and is intended for use only by Smith & Nephew and its manufacturer. It shall not be reproduced or copied in whole or in part, nor shall the contents be disclosed by any means without prior written permission from Smith & Nephew, nor shall anyone make any use of it that is contrary to the expressed or implied wishes of Smith & Nephew.

Study Protocol—Device	
A Multicenter, Post Market, Prospective Study Evaluating Safety and Efficacy of CONQUEST FN™ for the Treatment of Intracapsular Femoral Neck Fractures	Number: 18-3047-02
	Version: 2.0, 30Nov2018
	Page: Page 32 of 63

The ALSR assessment provides information about the ability of load transfer and motor control strategies in the lumbo/pelvic/hip complex. ASLR will be performed with the subject in a relaxed supine position with legs straight and feet apart. Subjects will be instructed to raise their operated leg 20cm above the examination table without bending the knee and without pelvic movement relative to the trunk. A score will be provided by the subject for the operated limb on a six-point Likert scale (0 = not difficult at all, 1 = minimally difficult; 2 = somewhat able to do, 3 = fairly difficult, 4 = very difficult, 5 = unable to do).

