## 9. STATISTICAL DESIGN

A Statistical Analysis Plan (SAP) will be written and finalized prior to database lock. The following is a brief description of the analyses to be described in this plan. The SAP will be more detailed and account for all analyses. All analyses will be conducted with statistical software SAS Version 9.4 or later.

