## **10. SAMPLE SIZE JUSTIFICATION**

Precision Analysis was used to assess the overall proportion of re-operation rate for any reason of displaced and non-displaced femoral neck fractures treated with the CONQUEST FN™ Femoral Neck Fracture System at one-year post-operation. Assuming a 5% lost to follow-up rate after the first year, a minimum of 90 subjects will be enrolled (based on the inclusion/exclusion criteria) in order to complete 80 evaluable subjects. The 90 subjects will be enrolled to allow a minimum of 45 subjects with each of the following indications to be recruited: displaced or non-displaced femoral neck fractures. For the displaced group this number of subjects is sufficient to estimate the proportion of success rate to within 12% by use of the two-sided 95% confidence interval (assuming an overall success rate of 87%). And for the non-displaced group this number of subjects is sufficient to estimate the proportion of success rate to within 10% use of the two-sided 95% confidence interval (assuming an overall success rate of 93%).

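### Level 2 of the active straight leg raise (ASLR) scale is worded as ability on a scale of difficulty, so its rank is ambiguous and ordered summaries of this secondary endpoint are hard to interpret

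*Combined protocol and SAP*

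**What the plan says.** The scale is defined once, in the ASLR assessment section (numbered 8.4.5 but printed at the end of Section 8.5). The subject, not the examiner, gives the score: "A score will be provided by the subject for the operated limb on a six-point Likert scale (0 = not difficult at all". The other five levels are "1 = minimally difficult; 2 = somewhat able to do, 3 = fairly difficult, 4 = very difficult, 5 = unable to do". Higher is worse. The section cites no source for the scale.

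Sections 8.4.4 and 8.4.5 (Exit Visit) tell sites to carry out the ASLR test as Section 8.5 instructs, at 6 weeks and at 3, 6 and 12 months.

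ASLR is one of twelve secondary endpoints. Section 9.4.2 introduces the list with "The rate or mean of the following outcomes at 1 year post-operation will be reported" and names "Active straight leg raise (ASLR) assessment" without saying whether a rate or a mean applies to it. Section 9.1 adds "Summary statistics will be given according to the nature of the variable, continuous or categorical" and does not assign ASLR to either type. Section 9 leaves the detail for later: "The SAP will be more detailed and account for all analyses".

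A smaller scale slip stands in Section 8.5.2, where the EQ-5D visual scale is described as "a numerical value from 1-100 where 0 is the worst imaginable health state".

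**The concern.** A self-rated ordinal scale works only if the respondent can place every label on one line from best to worst. Here the label at level 2 leaves that line. Being partly able to do a task can mean that the 20 cm lift was not completed. Fair or severe difficulty both suggest that it was completed, with effort. On that reading level 2 describes a worse state than 3 or 4 but carries a better score. A subject with difficulty between minimal and fair also finds no difficulty label to match.

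The harm arises when the data are collected. A later SAP can choose the summary, but it cannot recover what a subject meant by ticking 2. The study has no comparator (Section 6.1.2), so any misclassification goes straight into the single-arm estimate.

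**Working it through.** The plan gives no expected ASLR score, standard deviation, margin or sample size, so there is no figure to reproduce. The check sets the labels side by side, then shows what different readings of level 2 would do to a mean.

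**The labels, by what they grade**

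| Level | Grades | Implies the lift was done? |
|---|---|---|
| 0 | difficulty | yes |
| 1 | difficulty | yes |
| 2 | ability, partial | unclear |
| 3 | difficulty | yes |
| 4 | difficulty | yes |
| 5 | ability, none | no |

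Level 5 also uses ability wording, but it is plainly the worst state, so its rank is clear. Only level 2 puts an ability phrase among the difficulty grades. By contrast, the five EQ-5D-5L levels in Section 8.5.2 stay on one dimension throughout. No other section words level 2 differently.

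**Illustration 1: level 2 chosen for a worse state.** Let s be the share of subjects who choose level 2, and d the number of steps by which the state they mean lies above 2. The recorded mean is then too low by s × d. Both inputs are assumptions; the documents supply neither.

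| s | d = 0 (read as the step between 1 and 3) | d = 1 (means level 3) | d = 2 (means level 4) |
|---|---|---|---|
| 5% | 0 | 0.05 | 0.10 |
| 10% | 0 | 0.10 | 0.20 |
| 20% | 0 | 0.20 | 0.40 |
| 40% | 0 | 0.40 | 0.80 |

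**Illustration 2: level 2 avoided.** Suppose a share a of subjects has difficulty between levels 1 and 3, finds the label odd and ticks 3. The recorded mean is then too high by a × 1, which is 0.05 at 5% and 0.20 at 20%.

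**Illustration 3: full re-ranking.** Suppose level 2 really ranks between 4 and 5, so that 3 becomes 2, 4 becomes 3 and 2 becomes 4. Spread the other subjects evenly, r = (1 − s)/5 at each remaining level.

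- Printed mean = 2s + 13r, from 0 + 1 + 3 + 4 + 5 = 13.
- Re-ranked mean = 4s + 11r, from 0 + 1 + 2 + 3 + 5 = 11.
- Difference = 2s − 2r. At s = 5% the means are 2.57 and 2.29, a difference of −0.28. At s = 20% they are 2.48 and 2.56, a difference of +0.08. At s = 40% they are 2.36 and 2.92, a difference of +0.56.

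The sign changes with the assumed share and reading, so the direction is not determined.

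**Which summaries are affected.** A mean, a median, a rank-based test and a rate cut near levels 2 to 4 all need level 2 to have a known place. Counts per category do not, although the level 2 count itself stays hard to interpret.

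**What is not affected.** Section 10 sizes the study on another quantity: "Precision Analysis was used to assess the overall proportion of re-operation rate for any reason". ASLR does not enter it.

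**The case against.** The strongest reply is that subjects see a numbered scale. The codes rise from 0 to 5, and 2 stands between minimal and fair difficulty, so many subjects may read it as the step between them and no harm follows. That stands. It is why a reader who infers that the six answers are out of order goes further than the text allows: the rank of level 2 is ambiguous, not shown to be wrong.

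Three other replies also stand in part.

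- A reader might infer that the ASLR mean is invalid. Section 9.4.2 allows a rate or a mean, and Section 9.1 provides frequencies and percentages for categorical variables, so no mean is committed to. The ambiguity would weaken a mean if one were used.
- A reader might infer that the error flatters the device because a partly able subject scores low. That is one possible path. Subjects who avoid the label and tick 3 push the other way, and the plan sets no ASLR threshold or test.
- The CRF is not among the documents and may carry different wording. That is a reason to check it. The protocol text remains what sites are told to follow, and no sponsor form is named for ASLR as one is for Timed Up and Go in Section 8.5.3.

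The point that detail is left to a later SAP does not help, because the fault lies in the question put to the subject.

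**Conclusion.** The point holds as an ambiguity in one label of one secondary endpoint measured at four visits. Ordered summaries of ASLR are hard to interpret for answers given under the present wording.

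No size or direction can be given. A reader might take 0.1 to 0.4 points as the likely error, but that range needs 5% to 20% of subjects choosing level 2 and meaning a state two steps worse. The documents support neither input, and the range leaves out both the zero-shift reading and the readings that go the other way. The primary endpoint and the sample size are unaffected.

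The EQ VAS range is a separate and minor internal contradiction: zero is named as an anchor but lies outside the stated range.

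**What to change.** 1. In the ASLR section, reword level 2 as a degree of difficulty between levels 1 and 3, for example 'somewhat difficult', and leave the other levels as they are. Since no source is cited, check the wording against the instrument the sponsor meant to use.
2. Check that the CRF carries the same six labels.
3. Flag any scores already collected under the present label so that the two sets can be told apart.
4. In the SAP, state how ASLR will be summarised, and define the cut-point if a rate is used. Report the distribution over the six categories beside any mean.
5. In Section 8.5.2, change the EQ VAS range from 1–100 to 0–100, and check that the CRF agrees.

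The cost is a few words in the protocol and a form check. Section 14 reserves amendments after study start for exceptional cases and requires signatory and IRB approval, so the change could travel with another amendment. A change made mid-study also leaves two versions of the scale in the data, which the flag in step 3 handles.
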